## 7.9.2 Other Safety Evaluations

Adverse events of special interest, including any changes in vision and any events attributable to an embolic or ischemic cause (e.g., skin infarction), will be evaluated. Other safety evaluations are lip function, lip sensation, lip texture, lip firmness, lip symmetry, and lip movement/function.

#### 7.9.3 Definitions of Terms

#### 7.9.3.1 Adverse Event

An AE is defined as any untoward medical occurrence associated with the use of a drug/device in humans, whether or not considered drug/device-related (21 Code of Federal Regulations [CFR] 312.32 (a) and 803). An AE can therefore be any unfavorable and unintended sign (including an abnormal laboratory finding, for example), symptom, or disease temporally associated with the use of a drug/device, without any judgment about causality.

Expected adverse events are defined as the events that appeared at injection site subsequent to the first injection. Expected adverse events may include but are not limited to bruising, swelling, erythema, edema, and inflammation at injection site.

## 7.9.3.2 Suspected Adverse Reaction

A suspected adverse reaction (SAR) is defined as any AE for which there is reasonable possibility that the drug/device caused the AE (21 CFR 312.32 (a)).

#### 7.9.3.3 Unexpected Adverse Event

An AE or SAR is considered unexpected if it is not consistent with the risk information described in the labeling for the study device.

#### 7.9.3.4 Adverse Events of Special Interest

Certain events will require more detailed and timely reporting. These include:

- any significant changes in vision. A one-line change in the Snellen chart is considered significant and requires reporting as an AESI.
- any events attributable to an embolic or ischemic cause (e.g., skin infarction)
- Any incidence of an event due to an embolic or ischemic cause or visual disturbances (including, but not limited to, any loss of vision, blurry vision, double vision, pain in or around eye, blind spot or shadow in the visual field, trouble moving eyes, etc.) MUST be immediately reported to the Medical Monitor by phone, email or fax. The investigator/coordinator must complete the AE source/CRF page and email or fax it to the Medical monitor as soon as possible after the investigator or coordinator has become aware of its occurrence. These reports will include the depth of injection, the injection volume, the symptoms that were observed, the time to onset, time to resolution, and any

interventions that were implemented. The Sponsor will notify the FDA within 10 working days regardless of relation to investigational device.

In the event of blindness or any ophthalmic signs or symptoms, subjects will undergo immediate evaluation by a retina specialist.

Refer to Appendix 1: Filler First Aid Protocol.

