### 7.4.3 Study Device Administration

Subjects are physically masked (blindfolded) just prior to and during all injection procedures including the application of the LMX4 or inert cream to prevent observation of the syringes containing study device and the topical product. Any unblinded investigators and staff should be reminded NOT to discuss the treatment in the presence of the subject. Subjects will maintain the unique subject number previously assigned in Protocol PRO 2018-02 and PRO 2018-03.

The subject should be positioned in a seated position and may be reclined to as much as 45°.

Any makeup should be removed with a gentle cleanser or a specific makeup remover product (such as Neutrogena Cleansing Makeup Remover Facial Wipes).

The non-vermillion areas of the upper and lower lips should be prepared by gentle washing with a surgical scrub product (Chlorhexidine, Technicare, etc.).

To maintain the subject blinding, the upper and lower lip, upper and lower vermillion and any planned injection areas in or around the mouth corners should be covered with a liberal application of either the Sponsor provided inert cream or the topical anesthetic according to the randomization code. The designated cream product should be applied in a layer thick enough

that no skin or lip color is visible through the product. Investigators should use as much cream as necessary to achieve this result and not be limited to the contents of one tube of product.

Wait 15 minutes before treatment administration.

The anesthetic cream or inert cream should be removed by wiping firmly with a dry gauze before injecting. Only the area to be immediately treated should be wiped clear of cream. Areas not yet treated should remain covered with cream until moments prior to undergoing injection.

To prepare the syringes for use, the investigator should attach one of the needles included in the subject study device kit in a firm manner. The plunger should be gently depressed to express any unwanted air until a small droplet of implant material appears at the tip of the needle.

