## 7.4.4 Blinding of Study Device

Injections of the study device are performed by the unblinded Treating Investigator. The blinded Evaluating Investigator is not allowed to retrieve study supplies or to be present during opening of the study supplies or during the injections. The Treating Investigator is not to have any discussion with the Evaluating Investigator or subjects regarding the treatments.

Subjects are blinded to treatment assignment. Subjects are physically masked (blindfolded) just prior to and during all injection procedures to prevent observation of the syringes containing study device.

Subjects, investigators, the Sponsor's staff conducting the study, and members of the administrative team will not have access to individual subjects' treatment assignments. In the event of an emergency that requires breaking of the study blind, the randomization code will be maintained by each investigator that can be opened to reveal the study device.

See Section 7.9.10.2 for a description of the method of unblinding a subject during the study if such action is warranted.

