#### 7.6.5 Vision Evaluations

Subjects will be assessed with Snellen visual acuity, confrontational visual fields, and ocular motility by a trained evaluator. These assessments will be performed at Visit 1/Day 1 prior to treatment and repeated 30 minutes following treatment and at Visit 2/Month 1. Normal and abnormal findings are summarized in Appendix 5.

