## 7.7.1 Visit 1/Day 1: Treatment

Visit is  $\pm 14$  days of Day 168/Month 6 telephone call for PRO 2018-03 or for subjects enrolled from PRO 2018-02, Visit 1 is Day 1.

- Obtain written informed consent and read and sign the AESI letter dated 04JUN19.
- Update the medical history and demographic information as needed from entry to Protocol PRO 2018-02 and PRO 2018-03
- Perform vital signs (temperature, heart rate, blood pressure, and respiratory rate)
- Vision evaluation (Snellen visual acuity, confrontational visual fields, ocular motility)
- Obtain/record concomitant medications/treatments

- Evaluate inclusion/exclusion criteria
- Perform urine pregnancy test for all women of childbearing potential
- Reason for study participation question
- LFGS assessment
- POL assessment
- Lip function evaluation prior to treatment administration
- Lip sensation evaluation prior to treatment administration
- Lip texture evaluation prior to treatment administration
- Lip firmness evaluation prior to treatment administration
- Lip symmetry evaluation prior to treatment administration
- Lip movement/function prior to treatment administration
- pGAI assessment prior to treatment administration
- iGAI assessment prior to treatment administration
- Swelling assessment prior to treatment administration
- Subject satisfaction with lips (VAS) prior to treatment administration
- Treatment administration waiting 15 minutes after lidocaine cream or inert cream application
- Investigator Ease of Use assessment
- Subject Pain Score immediately after treatment (VAS)
- Subject Pain Score 15 minutes after treatment (VAS)
- Vision evaluation (Snellen visual acuity, confrontational visual fields, ocular motility) 30 minutes post treatment.
- Assess AEs
- Dispense subject diary card
- Schedule next visit
- Complete CRFs

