#### 7.9.5 Monitoring Adverse Events

Each subject will be monitored for the occurrence of AEs, including SAEs, immediately after treatment initiation. Each subject will be followed for safety monitoring until discharged from the study. Follow-up procedures related to pregnancy or AEs or SAEs may continue beyond the end of the study.

Subjects will be questioned and/or examined by the investigator or a qualified designee for occurrence of AEs throughout the study. The presence or absence of specific AEs should not be elicited from subjects. In addition, subjects will be instructed to record AEs on the subject diary card during the 2 weeks after treatment, and on the subject diary card dispensed at Visit 2 for the remainder of the study. Subjects having AEs will be monitored with relevant clinical assessments and laboratory tests, as determined by the investigator.

AEs, actions taken as a result of AEs, and follow-up results must be recorded on the CRF, as well as in the subject's source documentation.

For all AEs that require the subject to be withdrawn from the study and SAEs, relevant clinical assessments will be repeated as clinically appropriate until final resolution or stabilization of the event(s).

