## Preparation:

- The above materials should be gathered and labeled for emergency use only (to ensure they are available should an urgent situation arise).
- Staff should be educated regarding the urgent nature of such an event and the location of all materials and contact information.
- Investigators may wish to familiarize themselves with the retrobulbar injection technique via literature or on line training.

It is critical to recognize any intravascular events during injections and act quickly to maximize likelihood of reversal. As soon as an intravascular is recognized, **stop any further injections**.

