# If signs/symptoms of visual changes, opthalmoplegia, blindness, ocular pain (usually immediately) occur:

- Dispense Aspirin 325 mg Have patient chew or place the tablet sublingually for maximum rapid absorption
- Massage the globe with repeated inward compression and release this may free any embolic material
- Infiltration with hyaluronidase into area being corrected or augmented
- Have staff call ophthalmology: *Insert physician and cell phone number* or on-call ophthalmology at *nearest center with on-call ophthalmology*, and arrange transport
  - o Bring hyaluronidase with the subject to the ophthalmologist at least 300 units.
- If transport time to ophthalmology or ER is more than 60 minutes, consider performing retrobulbar hyaluronidase administration, 300-600 units at inferior, lateral orbital rim through orbital septum with 1-1.5 inch 27 gauge needle avoiding globe

  After above measures, expedite to emergency room, the retina can tolerate approximately 90 minutes of ischemia until damage becomes permanent.

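### Appendix 1's 60-minute transport trigger ignores elapsed time, so a visual sign first found at the scheduled 30-minute check can use up the appendix's own 90 minutes

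*Combined protocol and SAP*

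**What the plan says.** Section 7.9.3.4 sets the requirement once a sign appears: "In the event of blindness or any ophthalmic signs or symptoms, subjects will undergo immediate evaluation by a retina specialist". It then refers to Appendix 1, whose preparation notes say: "It is critical to recognize any intravascular events during injections and act quickly to maximize likelihood of reversal".

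Section 7.4.3 sets the conditions of injection: "Subjects are physically masked (blindfolded) just prior to and during all injection procedures including the application of the LMX4 or inert cream". Section 7.4.4 repeats the masking rule. No section sets a vision check or vision question for the moment the mask comes off.

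Section 7.6.5 gives the timing of the vision evaluations: "These assessments will be performed at Visit 1/Day 1 prior to treatment and repeated 30 minutes following treatment and at Visit 2/Month 1". The Visit 1 list in Section 7.7.1 agrees with this. Section 7.9.5 adds a general rule on adverse events: "The presence or absence of specific AEs should not be elicited from subjects". A direct question about vision changes exists, but only in the telephone contacts (Sections 7.7.2, 7.7.4 and 7.7.5).

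For visual symptoms, Appendix 1 lists aspirin, globe massage, local hyaluronidase, and a call to ophthalmology with transport. It continues: "If transport time to ophthalmology or ER is more than 60 minutes, consider performing retrobulbar hyaluronidase administration, 300-600 units". The same steps put the retina's tolerance at about 90 minutes before damage is permanent.

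**The concern.** The 60-minute trigger looks only at the journey ahead, whereas the 90-minute allowance runs from the occlusion. The two agree only if little time passes before the sign is recognized and the subject leaves the site.

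The protocol makes late recognition possible. A blindfolded subject cannot notice lost, blurred or double vision during the injections, although eye pain can be felt and blanching can be seen by the injector. The protocol's first eye-by-eye test after treatment comes 30 minutes later. A site could follow every instruction, find a sign at that check, face a journey of 60 minutes, and never be prompted to consider the retrobulbar step.

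The possible harm is permanent loss of vision. There is also a smaller effect on the safety record. Section 7.9.3.4 asks AESI reports for time to onset, and a loss that began under the mask can be dated only to when it was noticed. No efficacy analysis is affected.

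**Working it through.** The 90-minute figure is a clinical premise of Appendix 1. It cannot be derived from other inputs and is taken as given.

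**Inputs**
- Retinal tolerance: 90 minutes (Appendix 1, visual-change steps).
- Transport, T: 60 minutes, the longest journey that does not trigger the retrobulbar prompt (same steps).
- First scheduled vision evaluation after treatment: 30 minutes (Sections 7.6.5 and 7.7.1).
- Maximum session volume: 4.0 mL (Section 7.4.3).
- Flow rate not to be exceeded: 0.3 mL/min (Section 7.4.3, injection techniques).
- On-site first aid before departure, A: not stated. I take 0 as the best case and assume a range of 5 to 15 minutes.

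The 15-minute cream wait comes before any injection, so it is not counted.

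**Formulas**
- Arrival = E + A + T, where E is the time from occlusion to recognition.
- With T = 60, arrival by 90 minutes needs E + A ≤ 90 − 60 = 30.
- Shortest injection time = volume / 0.3. For 1.0 mL this is 3.3 minutes; for 4.0 mL it is 13.3 minutes.
- For a sign found at the scheduled check, E = 30 plus any injection time after the occlusion.

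**Results (minutes)**

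| Occlusion and recognition | E | Arrival, A = 0, T = 60 | Arrival, A = 5–15, T = 60 | Longest T for arrival by 90, A = 5–15 |
|---|---|---|---|---|
| Last injection, found at 30-minute check | 30 | 90 | 95–105 | 45–55 |
| Start of 1.0 mL, found at 30-minute check | 33.3 | 93.3 | 98.3–108.3 | 41.7–51.7 |
| Start of 4.0 mL, found at 30-minute check | 43.3 | 103.3 | 108.3–118.3 | 31.7–41.7 |
| Recognized at once | 0 | 60 | 65–75 | 75–85 |

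The scheduled check alone uses the whole 30-minute margin. If the sign is recognized at once, the 60-minute trigger works as intended.

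**Effect of a check at mask removal.** For an occlusion at the start of a 4.0 mL session injected at the ceiling rate, E falls from 43.3 to 13.3. Arrival becomes 13.3 + 60 = 73.3 minutes, or 78.3 to 88.3 with 5 to 15 minutes of first aid. A slower session would lengthen E, so the trigger also needs to count elapsed time.

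**The case against.** Much of the case on the other side stands, and it narrows the point.

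- **Earlier recognition is likely.** Appendix 1 itself notes that onset is usually at once. The subject looks in a hand mirror before further injections (Section 7.4.3) and marks a pain VAS immediately after injection and again at 15 minutes (Section 7.6.23). All of these need sight. What remains is loss in one eye or partial loss: the mirror and VAS can be managed with both eyes open, whereas the acuity and field tests in Section 7.6.5 cover one eye at a time.
- **The journey may be short.** Appendix 1 asks for the closest stroke-capable ER and, failing a named physician, the nearest center with on-call ophthalmology. No distances are given for the five sites, and no section caps them.
- **The retrobulbar step is not barred for shorter journeys.** It is worded as something to consider. Even so, a numeric trigger guides staff in an emergency, and this one omits elapsed time.
- **Section 7.9.5 is not a full barrier.** It allows general questioning and examination from the start of treatment. Only a specific vision question needs a stated exception.
- **Some sources are not available.** Section 7.9.9 mentions a treatment SOP, which may contain more. Appendix 1 is credited to a publication, so the basis of its 60 and 90 minutes cannot be checked here.

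A reader might infer that the protocol contradicts its own requirement for immediate evaluation. It does not: that requirement is triggered by a sign or symptom, so it runs from recognition. A reader might also infer that a compliant site leaves the subject untreated for 90 minutes. The text does not support that either. Aspirin, globe massage and hyaluronidase infiltration begin on site at recognition; what can pass 90 minutes is arrival at the specialist. Nor is the 30-minute evaluation a required delay. It is a backstop.

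**Conclusion.** The point holds as a gap in a safety procedure, at low to moderate severity. The trigger in Appendix 1 does not count elapsed time, and the first scheduled vision evaluation falls exactly where the remaining margin is zero. In an unlikely but protocol-compliant case, the subject reaches the specialist at 90 minutes, or at about 103 when the occlusion came at the start of 4.0 mL injected at the ceiling rate. The assumed first aid adds 5 to 15 minutes to either figure.

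This rests on three conditions: a loss not noticed at the mirror step or at either VAS mark, a journey close to 60 minutes, and the appendix's 90 minutes taken at face value. With 15 minutes of first aid, journeys of up to about 32 minutes meet the limit in every row of the table. The event should be rare, and nothing in the efficacy comparison changes.

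Appendix 1's contact list names on-call ophthalmology and an ER but no retina specialist, although Section 7.9.3.4 calls for one. That is a minor matter of alignment.

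**What to change.** 1. **Check at final mask removal.** When the mask comes off after the last injection, with syringes and cream out of sight, ask one question about vision and test finger counting with each eye separately. The Treating Investigator can do this, or the Evaluating Investigator once injections are over, since Section 7.4.4 keeps the latter away during them. State it as an exception to the Section 7.9.5 rule on eliciting specific events. Amend Sections 7.4.3, 7.6.1, 7.7.1 and 7.9.5, and keep the full 30-minute evaluation.
2. **Elapsed-time trigger in Appendix 1.** Prompt consideration of the retrobulbar step if time since possible onset (the first injection if unknown), plus on-site first aid, plus expected transport would approach 90 minutes. Keep the existing prompt for any transport over 60 minutes.
3. **Times on the CRF.** Record the start of injection and the removal of the mask, so that onset can be bounded in an AESI report.

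The cost is about a minute per subject, two CRF fields, limited rewording, and a slightly more frequent prompt to consider the retrobulbar step. Blinding is unaffected if syringes and cream are out of sight when the mask is lifted. The contact list can be aligned with Section 7.9.3.4 in the same amendment.

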#### 7.9.3.5 Serious Adverse Event

An SAE is defined as any AE or SAR that, in the view of the investigator or Sponsor, results in any of the following outcomes (21 CFR 312.32 (a)):

- Death
- Life-threatening AE (Note: the term "life-threatening" as used here refers to an event that in the view of the investigator or Sponsor places the subject at immediate risk of death at the time of the event; it does not include an AE or SAE that, had it occurred in a more severe form, might have caused death [21 CFR 312.32(a)])
- Inpatient hospitalization or prolongation of existing hospitalization. See exclusion to SAE reporting below under Planned Hospitalization.
- Persistent or significant incapacity or substantial disruption of the ability to conduct normal life functions
- Congenital anomaly/birth defect
- Required intervention to prevent permanent impairment/damage
- Any "other" important medical event. Important medical events that may not result in death, be life-threatening, or require hospitalization may be considered serious when, based upon appropriate medical judgment, they may jeopardize the subject and may require medical or surgical intervention to prevent one of the outcomes listed in this definition. Examples of such medical events include allergic bronchospasm requiring intensive treatment in an emergency room or at home, blood dyscrasias or convulsions that do not result in inpatient hospitalization, or the development of drug dependency or drug abuse.

The FDA considers events such as detached retina and Bell's Palsy serious adverse events.

#### 7.9.3.6 Planned Hospitalization

A hospitalization planned by the subject prior to signing the ICF is considered a therapeutic intervention and not the result of a new SAE and should be recorded as medical history. If the planned hospitalization or procedure occurs as planned, the record in the subject's medical history is considered complete. However, if the event/condition worsens during the study, it must be reported as an AE.

#### 7.9.4 Pregnancy

Pregnancies occurring after administration of study device require immediate reporting. They must be reported within 24 hours after the investigator has become aware of the pregnancy. A pregnancy report will be completed and sent by fax to the Sponsor or designee within 24 hours

of becoming aware of the pregnancy. The investigator will collect follow-up information regarding the outcome of the pregnancy and any postnatal sequelae in the infant that must also be reported to the Sponsor or designee. Upon awareness of the outcome of the pregnancy, the Principal Investigator or designee must forward a follow-up Pregnancy Report with any relevant information to the Sponsor or designee.

If the outcome of the pregnancy meets the criteria for immediate classification of an SAE (e.g., spontaneous abortion, stillbirth, neonatal death, or congenital anomaly), the investigator will report the event by faxing a completed SAE report form to the Sponsor or designee within 24 hours of being notified of the pregnancy report.

The subject should immediately be withdrawn from the study.

#### 7.9.5 Monitoring Adverse Events

Each subject will be monitored for the occurrence of AEs, including SAEs, immediately after treatment initiation. Each subject will be followed for safety monitoring until discharged from the study. Follow-up procedures related to pregnancy or AEs or SAEs may continue beyond the end of the study.

Subjects will be questioned and/or examined by the investigator or a qualified designee for occurrence of AEs throughout the study. The presence or absence of specific AEs should not be elicited from subjects. In addition, subjects will be instructed to record AEs on the subject diary card during the 2 weeks after treatment, and on the subject diary card dispensed at Visit 2 for the remainder of the study. Subjects having AEs will be monitored with relevant clinical assessments and laboratory tests, as determined by the investigator.

AEs, actions taken as a result of AEs, and follow-up results must be recorded on the CRF, as well as in the subject's source documentation.

For all AEs that require the subject to be withdrawn from the study and SAEs, relevant clinical assessments will be repeated as clinically appropriate until final resolution or stabilization of the event(s).

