#### 1 SYNOPSIS

**Title of Study:** A Multicenter, Double-blind, Randomized, Controlled, Roll-over Study of the Safety and Pain Associated with Injections of PN40082, RV001 with Topical Anesthetic or RV001 for Lip Augmentation

Name of Sponsor: Prollenium Medical Technologies Inc.

Name of Finished Product: PN40082®

**Device Composition:** PN40082 - Hyaluronic acid gel with lidocaine (0.3% w/w) RV001- Hyaluronic acid gel without lidocaine

**Objectives:** To evaluate the safety of repeat injections and pain associated with injection of PN40082 and comparative pain associated with RV001 with a topical anesthetic and RV001 for lip augmentation.

**Study Design:** This is a multicenter, double-blind, randomized, controlled, roll-over clinical study of treatment of subjects seeking lip augmentation who received treatment with either PN40082 or Restylane Silk in prior Protocol PRO 2018-02, and PN40082 in prior Protocol PRO 2018-03. Subjects meeting the inclusion/exclusion criteria will receive a single additional treatment with either RV001, RV001 with a topical anesthetic, or PN40082. The Evaluating Investigator will be blinded to the treatment. Injections of the study device will be performed by an unblinded Treating Investigator.

At each visit the blinded Evaluating Investigator evaluations and subject evaluations of the treated areas will be performed and recorded. Visits and telephone contacts will occur at:

Visit 1 / Day 1 — baseline and treatment

- Day 3 (±2 days) Safety follow-up telephone call
- Day 14 (±2 days) Safety follow-up telephone call

Visit 2 / Day 28 ( $\pm 2$  days) / Month 1 – End of Study Visit

- Day 56 (±4 days) / Month 2 Safety follow-up telephone call
- Day 168 (±7 days) / Month 6 End of Study telephone call

Efficacy evaluations are:

Subject pain score (VAS) at time of injection

Subject pain score (VAS) at 15 minutes after injection

Lip Fullness Grading Scale (LFGS) - overall lip fullness considering both lips together, fullness of the upper lip, and fullness of the lower lip

Perioral lines at rest severity scale (POL) - overall perioral lines at rest severity considering both lips together, perioral lines at rest severity of the upper lip, and perioral lines at rest severity of the lower lip

Patient Global Aesthetic Improvement (pGAI)

Investigator Global Aesthetic Improvement (iGAI)

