## 7 INVESTIGATIONAL PLAN

## 7.1 Overall Study Design

This is a multicenter, double-blind, randomized, controlled, roll-over study of the safety and pain associated with injections of PN40082, RV001 with topical anesthetic, or RV001 for lip augmentation.

Visits and telephone contacts will occur at:

Visit 1 / Day 1 - baseline and treatment.

- Day 3 (±2 days) Safety follow-up telephone call
- Day 14 (±2 days) Safety follow-up telephone call

Visit 2 / Day 28 ( $\pm 2$  days) / Month 1 – End of Study (EOS) Visit

- Day 56 (±4 days) Safety follow-up telephone call
- Day 168 (±7 days) End of Study telephone call

Efficacy evaluations are:

Subject pain score (VAS) at time of injection, 15 minutes after injection and at Visit 2.

Lip Fullness Grading Scale (LFGS) - overall lip fullness considering both lips together, fullness of the upper lip, and fullness of the lower lip

Perioral lines at rest severity scale (POL) - overall perioral lines at rest severity considering both lips together, perioral lines at rest severity of the upper lip, and perioral lines at rest severity of the lower lip

Patient Global Aesthetic Improvement (pGAI)

Investigator Global Aesthetic Improvement (iGAI)

Safety will be assessed by monitoring adverse events (AEs) at all study visits. Adverse events of special interest, including any changes in vision and any events attributable to an embolic or ischemic cause (e.g., skin infarction), will be monitored. Other safety evaluations are lip function, lip sensation, lip texture, lip firmness, lip symmetry, and lip movement/function.

Other evaluations are Investigator Ease of Use Assessment, Swelling Assessment, and Subject Satisfaction with Lips Assessment.

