### 7.5 Study Schedule

The visit-by-visit schedule of study activities is provided in Section 2. The timing of each visit is relative to Day 1, which is defined as the day the subject is treated in PRO 2019-02.

All visits should be performed within the windows specified on the schedule of study activities. Every attempt should be made to have each subject attend each visit as scheduled. If a subject is unable to attend a visit within the specified window the visit should be scheduled as closely as possible to the applicable window.

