## 7.7.2 Telephone Contacts on Day 3 and Day 14 ( $\pm$ 2 days)

- Assess AEs
- Assess concomitant medications/treatments
- Ask whether the subject is experiencing or has experienced any signs/symptoms of vision changes or stroke since the injection
- Confirm adherence to prohibited treatments/medications

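### The rule against eliciting specific AEs (7.9.5) conflicts with the scripted question at all four safety calls, and that question omits skin ischemia, a named AESI

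*Combined protocol and SAP*

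**What the plan says.** Section 7.9.5 (Monitoring Adverse Events) gives the general rule: "The presence or absence of specific AEs should not be elicited from subjects". It says should not rather than must not, but states no exception.

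Section 7.7.2 (Day 3 and Day 14 calls) lists this task: "Ask whether the subject is experiencing or has experienced any signs/symptoms of vision changes or stroke since the injection". Sections 7.7.4 (Day 56) and 7.7.5 (Day 168) repeat it.

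Section 7.9.3.4 defines AESIs as significant vision changes and events of embolic or ischemic origin, with skin infarction as the example. Section 7.1 commits to follow them: "any events attributable to an embolic or ischemic cause (e.g., skin infarction), will be monitored". Section 7.9.2 says they will be evaluated. Section 7.9.9 suspends enrollment and treatment at a site after a vascular embolic event that leads to any of three outcomes: skin necrosis, loss of vision or stroke.

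On timing, section 7.1 has "Day 3 (±2 days) Safety follow-up telephone call" and "Day 14 (±2 days) Safety follow-up telephone call", and section 7.5 counts from "Day 1, which is defined as the day the subject is treated in PRO 2019-02".

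**The concern.** There are two linked problems.

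First, asking about vision changes or stroke is asking about specific adverse events. A caller who follows the script departs from 7.9.5, and a caller who follows 7.9.5 leaves out a listed call procedure. The protocol does not say which governs, so staff at five sites are left to infer it.

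Second, the script covers only part of the AESI definition, and the general rule discourages a caller from adding the missing part. Safety of repeat treatment is a stated objective (section 6). If one AESI type is asked about by name at every call and another is not, their observed frequencies are not ascertained in the same way. A low count of skin-ischemic events would be harder to interpret than a low count of visual events.

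**Working it through.** **Step 1. The general rule against the call lists.**

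| Contact | Section | Asks by name about vision or stroke | Asks by name about skin ischemia |
|---|---|---|---|
| Day 3 call | 7.7.2 | yes | no |
| Day 14 call | 7.7.2 | yes | no |
| Day 56 call | 7.7.4 | yes | no |
| Day 168 call | 7.7.5 | yes | no |

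The conflict with 7.9.5 is present at 4 of 4 calls. It runs through the whole follow-up, on both sides of Visit 2.

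**Step 2. The script against the suspension triggers in 7.9.9.** The triggers are skin necrosis, vision loss and stroke. The script covers vision and stroke, so 2 of 3. The lists for Visit 1 (7.7.1), Visit 2 (7.7.3) and unscheduled visits (7.7.6) contain vision tests but no item naming skin ischemia, infarction or blanching. The omitted trigger is relevant to the treated site: the warnings in both Instructions for Use (Appendices 2 and 3) mention superficial necrosis after injection in or near vessels, and give the lips as an example.

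**Step 3. What can still pick up a skin event.**
- An open AE assessment is listed at every contact, and 7.9.5 has subjects questioned or examined for AEs throughout.
- The injection technique section (7.4.3) and Appendices 2 and 3 deal with blanching seen during or directly after injection.
- The diary takes any AE for 2 weeks (7.6.25). It is collected only at Visit 2, and recording an entry that persists past the last diary day as an AE is at the investigator's discretion (7.9.8).
- At Visit 2 the lips are examined in person for texture, firmness, sensation and function.
- Unscheduled visits are allowed at any time (7.7.6).

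The gap is therefore in targeted questioning only.

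**Step 4. The first-call window.** Inputs: Day 1 is the treatment day (7.5); first call Day 3 ± 2; second call Day 14 ± 2 (synopsis, 7.1, 7.7.2).
- First call: 3 − 2 = Day 1 to 3 + 2 = Day 5. The treatment day is inside the window.
- Second call: 14 − 2 = Day 12 to 14 + 2 = Day 16.
- Gap after a Day 1 call: 12 − 1 = 11 to 16 − 1 = 15 days.
- Gap at the nominal days: 14 − 3 = 11 days.
- For comparison, gap after a Day 2 call: 12 − 2 = 10 to 16 − 2 = 14 days.

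Excluding Day 1 would shorten the longest gap by 15 − 14 = 1 day. The Day 14 question looks back over the whole time since injection, so a treatment-day first call can delay learning of a vision or stroke event but does not remove it from the record.

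**The case against.** The strongest reply is that this is a drafting matter. Section 7.9.5 is the general AE rule and says only should not. Section 7.7 lists procedures required at each visit, and 7.9.3.4 sets AESIs apart for more detailed and timely reporting. On that reading the specific instruction governs and every site asks the question. This is reasonable and probably what was intended, but it is not written down, so the request to reconcile the text stands. It also leaves the omission of skin ischemia untouched.

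Several stronger readings are tempting, and the documents do not support them:

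- A reader might infer that AESI counts will differ between sites. That could happen if sites resolve the conflict differently, but nothing shows that it will. The script is the same in every arm, so no between-arm bias is shown either.
- A reader might infer that skin ischemia is found only if the subject volunteers it. The routes in step 3 contradict this. Every subject also signs an AESI letter (7.6.2). Its content is not in the documents, so what subjects are told about skin events is unknown.
- A reader might link the early call to the 24-hour step for persisting blanching in Appendix 1. That step applies to an infarction already identified and under monitoring, and does not depend on a scheduled call.
- A reader might treat the window as a cause of lost events. Step 4 shows that it affects timing.

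Nor do the documents make AESI counts a headline output: section 8.3 plans TEAEs by preferred term, plus a separate summary of visual-related events.

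**Conclusion.** The concern holds in a limited form. The contradiction is plain on the text and affects all four calls. The scripted question covers two of the three embolic outcomes in 7.9.9 and omits the skin outcome, although skin infarction is the protocol's own example of an embolic or ischemic AESI. The consequence is unequal ascertainment: visual and stroke events are solicited, skin-ischemic events are not. No event count or bias can be calculated from the documents, and none is claimed.

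This rests on two assumptions: that the contact lists in 7.7 are complete, and that no separate call script or training material supplies the missing exception or question. The treatment-day window is a minor timing point.

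**What to change.** 1. In 7.9.5, add an exception for AESIs that are asked about with the scripted call questions in 7.7.2, 7.7.4 and 7.7.5.
2. In those three sections, extend the scripted question to signs of skin ischemia at or near the treated area, so that it matches the AESI definition in 7.9.3.4 and the outcomes in 7.9.9.
3. In the data and tables, label solicited AESIs separately from spontaneously reported AEs. This matters because the synopsis plans to compare AE incidence across three studies, and the documents do not say what was asked at contacts in the two earlier ones.
4. As a minor item, reconcile the Day 3 (±2 days) window with the definition of Day 1 and with the call's purpose as follow-up.

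The cost is protocol and call-script wording plus one label in the data, with no added contact or examination. The downside is that solicited AESI counts may rise slightly, which the labelling makes visible.
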